## Statistical Analysis Plan

This Statistical Analysis Plan (SAP) details the statistical methodology to be used in analyzing clinical trial data and outlines the statistical programming specifications, tables, figures, and listings for clinical trial POX-MVA-037. It describes the variables and populations, anticipated data transformations and manipulations, and other details of the analyses not provided in the clinical trial protocol (CTP).

This SAP will be followed completely for the analysis of data derived from the clinical trial POX-MVA-037. If any unforeseen additional analysis is included in the clinical study report (CSR) they will be clearly flagged as an additional unplanned analysis.

The analyses described are based on the final CTP for POX-MVA-037 ([Doc. No. 92000015](#)) Edition 5.0 dated 18 November 2014.

## General Definitions

### Enrolled Subjects

Subjects are considered enrolled once they have received the first trial vaccine injection.

### Vaccination

For this trial, vaccination means the subject received all planned injections of MVA-BN® at the respective visit, i.e. a single injection per visit for subjects in Group 1 and Group 3, and two injections per visit for Group 2 constitute a vaccination (see [Section 1.1](#)).

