### **Vaccination Period**

A vaccination period is defined as the period of time starting after each vaccination (for Group 2: after the first injection) and ending 28 days after the vaccination, or, if it occurs first, until the subject receives another vaccination or discontinues the trial (see [Table 1](#)).

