### Subjects Receiving All Vaccinations

A subject received all doses of trial vaccination according to the randomized group assignment if a date of drug administration is given for the vaccination at Visit 1, Visit 3, and in addition in Group 3 for the vaccination at Visit 6, and no major deviation is recorded on the electronic Case Report Form (eCRF).

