### 3.2 Analysis Populations

#### 3.2.1 Full Analysis Set (FAS)

This is the subset of subjects who received at least one injection and for whom any data are available.

The main analysis of safety will be performed on this analysis set.

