### **3.5.7 Compliance**

Compliance will be evaluated with respect to the number vaccinations received and the number of memory aids completed.

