#### Solicited Local AEs

Solicited local AEs will be summarized by PT after each vaccination visit, and broken down by maximum intensity.

In addition, the incidence will be calculated by severity (i.e. the number of subjects developing a particular local solicited AE during the 8-day period after each vaccination divided by the number of subjects actually receiving this vaccination) with corresponding 95% Clopper-Pearson CI. The incidence will also be calculated for any solicited local AE for each vaccination period and per subject.

The duration of the AEs will be included in the listing. The duration of the AEs will also be summarized using the mean, SD, median, minimum and maximum.

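### The SAP counts a Group 2 vaccination only when both injections are given, so a subject given one of two leaves the per-vaccination solicited-AE denominator and, at Visit 3, can have events misclassified

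*SAP*

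**What the plan says.** The SAP's General Definitions treat an injection and a vaccination as different things. A vaccination requires every injection planned for the visit: "vaccination means the subject received all planned injections of MVA-BN ® at the respective visit". For the double-dose arm, "two injections per visit for Group 2 constitute a vaccination". In Groups 1 and 3 one injection is one vaccination, so the two terms coincide there.

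The SAP then uses both units.

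- **By injection:** enrolment, trial day, the window for a treatment-emergent AE, the SAE listing in 3.5.3, and the FAS in 3.2.1 ("This is the subset of subjects who received at least one injection and for whom any data are available").
- **By vaccination:** the solicited local AE incidence in 3.5.9 ("divided by the number of subjects actually receiving this vaccination"), which is carried over to solicited general AEs; the 8-day rule in 3.3.2 that separates solicited from unsolicited AEs; the 28-day rule in 3.5.9 that decides entry to the summary tables; and compliance (3.5.7).
- **Mixed:** the vaccination period runs "starting after each vaccination (for Group 2: after the first injection) and ending 28 days after the vaccination".

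The definition of Subjects Receiving All Vaccinations is met "if a date of drug administration is given for the vaccination at Visit 1, Visit 3, and in addition in Group 3" at Visit 6, provided no major deviation is recorded in the eCRF. It does not mention the number of injections.

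**The concern.** Only Group 2 has two injections planned per visit, so only Group 2 can be partly dosed. Suppose a Group 2 subject receives one injection at a visit and not the other. By the SAP's own definition that visit contains no vaccination, yet the subject was exposed and can react. Rules keyed to injection keep the subject and the event; rules keyed to vaccination do not.

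The trial's primary objective is safety when the dose or number of injections is raised. If a second injection is not given because of a reaction to the first, that subject is especially informative about the double-dose regimen. A literal reading removes this subject from the rate meant to describe reactogenicity after that visit, and it can do so in one arm only.

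**Working it through.** **1. Denominator.** The solicited-AE rate divides by subjects who received the vaccination, and a Group 2 vaccination means both injections. A subject given one of two is therefore not counted. With 30 planned in Group 2 and k partly dosed at a visit, the denominator is 30 − k.

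**2. Event timing after a partial dose at Visit 3.** Visit 3 falls 28 to 35 days after Visit 1. If only one injection is given at Visit 3, the previous vaccination in the SAP's sense is still the one at Visit 1. An event starting d days after the Visit 3 injection therefore starts at least 28 + d days after it.

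- *8-day rule (3.3.2), Days 0 to 7:* 28 + d is above 7 for every d ≥ 0. Every solicited symptom is reclassified as unsolicited, whatever its preferred term.
- *28-day rule (3.5.9):* 28 + d is above 28 for every d ≥ 1. For d = 0 the event stays inside only if Visit 3 is exactly on Day 28. Almost every event is left out of the summary tables and flagged as non-treatment emergent.
- *Treatment Emergent Adverse Event definition:* the window runs 28 days from injection, so the same event is treatment emergent.

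The last two rules give opposite answers for one event. The bracket in the vaccination-period definition moves the start to the first injection, but the period still ends 28 days after a vaccination that did not take place. The 8-day and 28-day rules contain no such bracket.

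**3. The plan's safety figure.** SAP 3.1 states at least 95% probability of seeing an AE of incidence 1 in 10 with 30 subjects. Check: 1 − 0.9^30 = 95.8%, so it reproduces. With 30 − k subjects (k is assumed):

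| k | n | 1 − 0.9^n |
|---|---|---|
| 0 | 30 | 95.8% |
| 1 | 29 | 95.3% |
| 2 | 28 | 94.8% |
| 3 | 27 | 94.2% |

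**4. Effect on a rate.** Assume 15 of 30 Group 2 subjects report a given solicited AE (Clopper-Pearson 95% CI in brackets).

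| Handling | Rate |
|---|---|
| All injected subjects counted | 15/30 = 50.0% (31.3 to 68.7) |
| k = 1, no event in that subject, or event kept in the numerator | 15/29 = 51.7% (32.5 to 70.6) |
| k = 1, event removed with the subject | 14/29 = 48.3% (29.4 to 67.5) |
| k = 2, no events in them, or events kept in the numerator | 15/28 = 53.6% (33.9 to 72.5) |
| k = 2, both had the event and are removed | 13/28 = 46.4% (27.5 to 66.1) |

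**5. Adherence.** The all-vaccinations definition asks for an administration date per visit and no recorded major deviation. Under SAP 3.2.2 a major administration deviation is an example of a major violation, but major or minor is settled case by case at the data review meeting. No rule says how a missed second injection is to be rated. Compliance in 3.5.7 counts vaccinations and memory aids, so it would not show one explicitly.

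**The case against.** The strongest reply is that the SAP's safety frame rests on injections. Enrolment, the FAS, the treatment-emergent window and the SAE listing all start from injection. SAEs and AESIs in the active and follow-up phases are treatment emergent whatever their onset day. All of this stands. A reader might infer that a partly dosed subject drops out of the safety analysis as a whole; the documents do not support that. The general AE incidence in 3.5.9 divides by subjects at the time of vaccination, which is ambiguous rather than clearly restrictive.

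A second reply is that the bracket for Group 2 opens the period at the first injection, and that the vaccination definition is only a counting rule: two injections, one vaccination. The first part stands for the start of the period. Neither part changes the solicited-AE denominator or the two rules that run from the previous vaccination. The definition also says in terms that all planned injections were received.

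A reader might also infer that one administration date is enough for a partly dosed subject to pass as fully vaccinated. It is not: no major deviation may be recorded, and the Per Protocol Set (PPS) itself requires all vaccinations. Entry is possible only if the missed injection is not rated major.

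A sole event in one partly dosed subject might be shown as 1/30 (0.1% to 17.2%) falling to 0/29 (0% to 11.9%). That assumes the event disappears from the numerator, whereas the treatment-emergent definition keeps it and the AE listings show it.

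Finally, the protocol's FAS (9.3) speaks of a vaccination and the SAP's of an injection. Calling that a conflict reads the SAP's definition back into the protocol, which does not contain it.

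**Conclusion.** The point holds in a limited form. Read as written, the SAP excludes a partly dosed Group 2 subject from the per-vaccination solicited local and general AE denominators. For a partial dose at Visit 3, it also gives contradictory instructions on whether that subject's events are solicited, treatment emergent and tabulated. How such a subject is handled for the PPS is left to judgement, not fixed in advance.

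The size depends on whether partial dosing occurs, and the documents report no count. In the assumed example, one such subject shifts a 50% rate by less than 2 percentage points and two shift it by less than 4, far inside the confidence intervals. The reason to act is that the ambiguity falls only on the double-dose arm, bears on the safety objective, and is easily removed.

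**What to change.** Amend the SAP wording as follows.

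1. Define the vaccination period, the 8-day and 28-day windows and every AE denominator from receipt of at least one injection at the visit. This touches the Vaccination Period definition, 3.3.2, and the incidence and 28-day rules in 3.5.9, including solicited AEs.
2. In Subjects Receiving All Vaccinations, require the planned number of injections to be recorded at each visit (two per visit for Group 2), so that a missed injection is treated the same way for every subject when the PPS is formed.
3. Optionally, align the FAS wording of protocol 9.3 and SAP 3.2.1 with a line in SAP 3.6. An injections-received column in Table 15.1.5.1 and a separate listing of partly dosed subjects would also help but are not essential.

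The cost is text and programming specification only. Listing 16.2.1.5.2 already plans product administration data; that it records each injection separately is an assumption to confirm. No trial procedure changes.

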### Injection

An injection refers in this trial to a single injection with the trial vaccine.

### Trial Day

The individual subject's day of trial is calculated from the day of the first injection. The day of first injection is defined as Day 0 and the day after first injection is Day 1, and so on. Equally, the day before first injection is defined as Day -1, and so on. In particular, no reference is made to the time of the injection in the calculation of the trial day, i.e. at midnight a new trial day begins regardless of the time of first injection. Note that it is possible for Visit 1 to be performed, for example, on trial Day -1.

### Baseline

If not otherwise specified, 'Baseline' refers to the last measurement before the first injection of trial drug for a given parameter. This is either at Visit 1 or Screening Visit (SCR), or latest re-screening as appropriate. If there is missing vital sign data at Visit 1 then data obtained at the Screening Visit or latest re-screening visit will be used to impute the missing data. These data

will be summarized as Baseline data without specification of which visit was used. However, at all other visits no imputation will be used and the actual visit used will be specified in tables or listings.

### **Screening Phase**

The screening phase is defined from the Screening Visit up to Visit 1 before the first injection. This includes any re-screening visits that are conducted.

### **Vaccination Period**

A vaccination period is defined as the period of time starting after each vaccination (for Group 2: after the first injection) and ending 28 days after the vaccination, or, if it occurs first, until the subject receives another vaccination or discontinues the trial (see [Table 1](#)).

### **Pre-Booster Period**

The pre-booster period applies only to Group 3 and is defined as the period of time starting at completion Visit 5 up to Visit 6 before the booster vaccination (see [Table 1](#)).

### **Active Trial Phase**

The active trial phase covers the period from the first injection until the beginning of FU phase (see [Table 1](#)). Hence:

- For Group 1 and 2 the active trial phase is the time period between Visit 1 and 5 (starting with the first injection on Visit 1 and including Visit 5). Specifically, this includes possible periods where the second vaccination is 29 days or longer after the first vaccination (i.e. between Day 28 after the first vaccination until the second vaccination), and where Visit 5 is 29 days or longer after second vaccination (i.e. between Day 28 after the second vaccination until Visit 5).
- For Group 3 the active trial phase is the time period between Visit 1 and 8 (starting with the injection on Visit 1 and including Visit 8). This includes
  - possible periods where the second vaccination is 29 days or longer after the first vaccination,
  - possible periods where Visit 5 is 29 days or longer after the second vaccination,
  - the pre-booster period from completion of Visit 5 until the vaccination at Visit 6, and
  - possible time periods where Visit 8 is 29 days or longer after the third vaccination.

### **Treatment Phase / Overall Vaccination Period**

The treatment phase is defined as the sum of all vaccination periods for each subject (see [Table 1](#)). This means the treatment phase comprises:

- for Groups 1 and 2 the sum of vaccination periods 1 and 2.

- for Group 3 the sum of vaccination periods 1, 2 and 3.

### FU Phase

All data collected after completion of Visit 5 (Groups 1 & 2) or Visit 8 (Group 3) until, and including, the 1 year Follow-up (FU 2) Visit. Note that for some subjects for whom the six months FU 1 Visit was not performed there may be FU 2 data available. Missing FU 1 or FU 2 Visit data will be considered a minor protocol violation (see [Table 1](#)).

**Table 1 Schematic presentation of trial phases**

Group	Active Trial Phase							FU Phase	
	Vacc. Period 1	Day 2 9 – Visit 3	Vacc. Period 2	Day 29 – Visit 5	Pre-Booster Period	Vacc. Period 3	Day 29 – Visit 8	Visit 5 or 8 – FU 1	FU 1 – FU 2
	X		X			(X)			
	Belongs to Treatment Phase / Overall vaccination period								
1 & 2	Yes	No	Yes	No	N/A	N/A	N/A	No	No
3 only	Yes	No	Yes	No	No	Yes	No	No	No

X: vaccination occurs at the beginning of the respective period; (X) Group 3 only

### Eligible Subjects

A subject is eligible if the question “is the subject eligible for the trial?” is answered with “yes” and there are no subsequent major protocol deviations that affect the eligibility of the subject.

### Subjects Receiving All Vaccinations

A subject received all doses of trial vaccination according to the randomized group assignment if a date of drug administration is given for the vaccination at Visit 1, Visit 3, and in addition in Group 3 for the vaccination at Visit 6, and no major deviation is recorded on the electronic Case Report Form (eCRF).

### Treatment Emergent Adverse Event

An adverse event (AE) with onset either on the day of a vaccination, but after injection, or within the 28 days following injection. AEs recorded outside the 28 day window after the last injection of trial vaccine will be classified as non-treatment emergent AEs.

### Pre-treatment Adverse Events

AEs recorded after the signing of the informed consent form but before the first injection of trial vaccine are considered pre-treatment AEs.

### Non-treatment Emergent Adverse Events

Events recorded in the active trial phase but not in the treatment phase. New non-serious or non-special interest AEs according to protocol will not be recorded in the FU phase. However, should any such events be recorded they will also be considered as non-treatment emergent. The classification of AEs into treatment emergent or non-treatment emergent will be decided based on the onset date/time of the AE.

Note that all Serious Adverse Events (SAEs) and Adverse Events of Special Interest (AESIs) within the active and FU phases are considered treatment emergent. SAEs and AESIs within the screening phase are considered non-treatment emergent.

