##### Criteria:

The following criteria should be checked prior to second/booster vaccination. If any are applicable, the subject should not receive any further vaccination(s):

- Any clinically significant cardiac sign and symptom (i.e. AESI) defined in [Section 8.1.2.3](#).
- An AE that, in the opinion of the investigator, makes it unsafe for the subject to receive a further vaccination. In this case, the appropriate measures will be taken.
- Anaphylactic reaction following the administration of any vaccine(s).
- Clinical need for concomitant or ancillary therapy not permitted in the trial, i.e.
  - Vaccination with any licensed live vaccine within 30 days prior or after trial vaccinations or any licensed killed vaccine within 14 days prior or after trial vaccinations
  - Start of chronic systemic administration (defined as more than 14 days) of > 5 mg prednisone (or equivalent) per day or any other systemic use of immune-modifying drugs.
  - Administration of immunoglobulins and/or any blood products.
- Use of any investigational or non-registered drug or vaccine other than the trial vaccine.
- Pregnancy
- Subject refuses to receive second vaccination.
- Any condition which contradicts administration of the second vaccination in the opinion of the investigator.

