### 3.5.9 Adverse Events

For the treatment phase analysis a summary table will be presented of the number (and percentage) per vaccination period both per subject and for the number of events for the following events:

- Any AEs
- Any TEAEs
- ADRs (Adverse Drug Reactions)
- Treatment emergent ADRs; note that all local solicited AEs are automatically considered ADRs
- Severe TEAEs (Grade 3 or higher, for grading please refer to the CTP)
- Severe ADRs (ADR graded 3 or higher, for grading please refer to the CTP)
- SAEs
- AESIs
- AEs leading to withdrawal from vaccination
- Deaths

In addition, the incidence of AEs will be calculated (i.e. the number of subjects developing a treatment emergent AE divided by the number of subjects at the time of the vaccination) with corresponding 95% Clopper-Pearson CI. The incidence of any AE will also be calculated for each vaccination period, overall vaccination period and per subject.

For analysis of the treatment phase the information will be based on the data provided from Visit 1 to Visit 5, and additionally Visit 6 to Visit 8 for Group 3.

For the treatment phase, all AEs will be listed by subject, including demographic information, SOC and PT. Any AE with onset later than 28 days after the previous vaccination will not be included in summary tables but will be included in the listing and will be flagged accordingly as non-treatment emergent.

According to the CTP no new AEs should be reported during the FU phase, except SAEs and AESIs, but if any are reported then they will be listed but considered non-treatment emergent.

The number of subjects with at least one treatment emergent AE during the treatment phase will be descriptively compared between the treatment groups, and between vaccination periods within Group 3.

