#### Unsolicited AEs

Treatment emergent unsolicited AEs will be summarized by SOC and PT and vaccination period and by subject.

A summary of the number of AEs by intensity and by relationship to trial vaccination will also be presented.

The number of AEs with a reasonable possibility of being related to the vaccine will be presented in a separate listing and summarized in a table by SOC and PT and vaccination period and by subject.

Non-treatment emergent AEs will only be flagged and included in the listing, but will not be included in the tables.

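### SAP 3.5.9 drops from its AE-withdrawal row any non-serious, non-AESI event that starts more than 28 days after a dose and blocks the next one, which mainly affects the Group 3 booster

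*SAP*

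**What the plan says.** The SAP General Definitions end a vaccination period 28 days after the dose, or earlier if another dose or discontinuation comes first. The treatment phase is the sum of these periods. SAP Table 1 marks the stretches from Day 29 to Visit 3 and from Day 29 to Visit 5, and the pre-booster period, as outside it. On the last of these: "The pre-booster period applies only to Group 3 and is defined as the period of time starting at completion Visit 5 up to Visit 6".

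Non-treatment emergent AEs are defined as "Events recorded in the active trial phase but not in the treatment phase". The test is timing, not consequence: "The classification of AEs into treatment emergent or non-treatment emergent will be decided based on the onset date/time of the AE". There is one carve-out: "all Serious Adverse Events (SAEs) and Adverse Events of Special Interest (AESIs) within the active and FU phases are considered treatment emergent".

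SAP 3.5.9 then plans a treatment-phase overview by vaccination period, with a row for "AEs leading to withdrawal from vaccination". Further down, the section states: "Any AE with onset later than 28 days after the previous vaccination will not be included in summary tables". These events go to a flagged listing. The Unsolicited AEs part repeats the rule: "Non-treatment emergent AEs will only be flagged and included in the listing, but will not be included in the tables".

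Protocol 4.2.5 has the withdrawal criteria checked before the second and the booster dose. One of them is: "An AE that, in the opinion of the investigator, makes it unsafe for the subject to receive a further vaccination". It carries no limit on when the event began.

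**The concern.** A 28-day window suits a rate of events after a dose. It does not suit a row defined by what the event led to, namely a dose not given. The decision to withhold is made at Visit 3 or Visit 6, and an event that began shortly before Visit 6 lies outside every vaccination period. The row would then omit an event of exactly the kind that its label describes.

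Only Group 3 has a booster to withhold, so the omission is unequal between arms in a trial whose primary objective is safety when doses are added. Two planned tables could also disagree: the disposition table would show a booster withheld for an AE, and the AE overview would show no AE leading to withdrawal. A reader would then have to match listings by hand to find the event's term, grade and relationship to vaccine.

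**Working it through.** **The plan's own figure.** The plan states no number on this point. Its one numerical safety claim (Protocol 9.2, SAP 3.1) is a detection probability of at least 95% for an AE of 1-in-10 incidence with 30 subjects: 1 − 0.9^30 = 0.958. This reproduces and is not affected.

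**Which events drop out.**
1. Onset more than 28 days after dose 2 and before Visit 6: outside all vaccination periods (General Definitions, SAP Table 1).
2. It cannot be a solicited AE. SAP 3.3.2 treats any listed symptom that starts outside the 8-day window as unsolicited.
3. If it is neither an SAE nor an AESI, the carve-out does not apply and it is non-treatment emergent.
4. If its start date is complete, the worst-case rule in SAP 3.3.2, which counts AEs with partly missing start dates as treatment emergent, does not apply either.
5. SAP 3.5.9 therefore sends it to the listing and keeps it out of summary tables, including the row in question. The definition in step 3 only classifies; the sentence in 3.5.9 does the excluding.

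**Length of the gap.** Inputs from the visit schedule (Protocol 1.5 and 1.6): Visit 3 on Day 28 to 35, Visit 6 on Day 84 to 96.
- Before the booster, gap = Visit 6 − Visit 3 − 28.
  - Target: 84 − 28 − 28 = 28 days.
  - Shortest: 84 − 35 − 28 = 21 days.
  - Longest: 96 − 28 − 28 = 40 days.
- As a share of the dose 2 to booster interval: 28/56 = 50%, with a range of 21/49 = 43% to 40/68 = 59%.
- Before dose 2, all groups, gap = Visit 3 − 28: 28 − 28 = 0 to 35 − 28 = 7 days.

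**Effect on the row.** Assume all 30 Group 3 subjects are in the denominator and x of them have such an event. The documents give no value for x. If no other event qualifies, the row shows 0/30 = 0% (Clopper-Pearson 95% CI 0 to 11.6%) in place of:
- x = 1: 1/30 = 3.3% (0.1 to 17.2%)
- x = 2: 2/30 = 6.7% (0.8 to 22.1%)
- x = 3: 3/30 = 10.0% (2.1 to 26.5%)

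**The case against.** Several objections carry weight.

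- **These subjects never received the booster.** A reader might infer that the booster regimen will look better tolerated than it was. The documents do not support that. At onset such a subject has had the same two standard doses as Group 1, the second more than 28 days earlier, so the event says nothing about reactions to a third dose. This stands and limits the point to completion of the regimen.
- **The withheld dose is still reported.** A reader might also infer that it vanishes. It does not. SAP 3.5.4 and Table 15.1.1.2 count withdrawals from the third vaccination with primary reasons and no onset window. Subject listings give the reason, and the event appears in flagged AE listings. With 30 per group these can be read directly. This stands, but SAP 3.5.4 promises no AE term, grade or relationship, and the two tables can still conflict.
- **The SAP is not of one mind.** The overview separates a row for any AE from one for treatment emergent AEs, and the withdrawal row carries no treatment emergent label. A programmer might include these events. The general exclusion in the same section nevertheless forbids it, so the ambiguity is itself a reason to state the rule.
- **The row is not an endpoint.** This is correct. The secondary endpoint for unsolicited non-serious AEs itself uses 28 days after each vaccination, so the window is sound for that purpose.
- **The 50% share depends on the interval chosen.** Protocol 4.2.5 sets no onset limit, so a blocking event may start after dose 1. Measured from Day 0 to Day 84 the share is 28/84 = 33%. The length of the gap in days does not depend on this choice. Any probability that an event is missed would need a number of affected subjects and an onset pattern, and the documents give neither.
- **A fuller count has no comparator.** New non-serious AEs stop being collected at Visit 5 in Groups 1 and 2, so counting to Visit 6 in Group 3 adds background illness. This stands and is met by the split and footnote proposed below.

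**Conclusion.** The point holds in a limited form. Read literally, SAP 3.5.9 leaves out of its AE-withdrawal row any non-serious, non-AESI event with a complete start date that begins more than 28 days after the preceding vaccination and causes the next dose to be withheld. With 21 to 40 uncounted days before the booster against 0 to 7 before dose 2, the undercount falls almost only on Group 3. Each omitted subject costs 3.3 percentage points if the denominator is 30. How many there would be is unknown.

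The consequence is an understated count of AE-related failure to complete the three-dose regimen and a possible mismatch with Table 15.1.1.2. It does not extend to the tolerability of the booster itself, to SAEs or AESIs, or to the sample size.

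**What to change.** State in SAP 3.5.9 that the AE-withdrawal row:
- counts every AE with onset from first injection to the end of the active trial phase that led to withdrawal from the second or booster vaccination;
- is exempt from the 28-day exclusion from tables, in both places where that exclusion appears;
- is split by onset within or after 28 days of the preceding vaccination, with the Group 3 pre-booster period shown separately;
- is reconciled with the withdrawal reasons in Table 15.1.1.2.

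Add a footnote that Groups 1 and 2 have no comparable pre-booster period, so the late-onset part of the Group 3 count has no comparator.

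The cost is a short SAP addition and one programming exception. No new data are needed, because Protocol 8.2.5 already has Group 3 AEs recorded through Visit 8. No clinical rule, endpoint or sample size changes. The Group 3 count may come out slightly less favourable.
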